7.6 Methods for Clinical Procedures

Not applicable.

8. CRITERIA FOR EVALUATION AND ENDPOINT DEFINITION

8.1 Primary Endpoint

The primary endpoint is the persistence and stability of serologic GMT of HPV16/18 between 6, 12, 18 and 24 months after the prime dose/prior to administration of the second dose.

8.2 Secondary Endpoints

The secondary endpoints include

- Determination of the persistence and stability of serologic GMT of other carcinogenic HPV types 31/33/45/52/58 and non-carcinogenic HPV 6/11 between 6, 12, 18, and 24 months.
- Assessment of safety and reactogenicity to each vaccine dose.

8.3 Off-Agent Criteria

Participants may stop taking study agent for the following reasons: completed the protocol-prescribed procedures, adverse event or serious adverse event, received an HPV vaccine outside the context of the study, inadequate agent supply, noncompliance, concomitant medications, and medical contraindication. Participants will continue to be followed, if possible, for safety reasons and in order to collect endpoint data according to the schedule of events. Participants who have received HPV vaccine outside the context of the study will be taken off study,

8.4 Off-Study Criteria

Participants may go ‘off-study’ for the following reasons: the protocol procedures and any protocol-required follow-up period is completed, adverse event/serious adverse event, lost to follow-up, non-compliance, concomitant medication, medical contraindication, withdraw consent, death, determination of ineligibility (including screen failure), pregnancy, or have received HPV vaccine outside the context of the study.

8.5 Study Termination

NCI, DCP as the study sponsor has the right to discontinue the study at any time.

9. CORRELATIVE/SPECIAL STUDIES

9.1 Rationale for Methodology Selection

HPV16 and HPV18 serology will be determined by VLP ELISA assays as previously described [16-18]. This ELISA assay is a standard measure of immunogenicity, measures total levels of HPV16 and 18 specific IgG antibodies, both neutralizing and non-neutralizing, and is amenable for use in large epidemiologic and clinical studies.

Serology of HPV types 6/11/31/33/45/52/58 will be determined using CLIA/ELISA assays when the assays are developed and made available.

9.2 Comparable Methods

The VLP ELISA assays have been used previously to measure HPV16/18 serology in prior HPV vaccine trials [19-22]. We will be able to compare the serology data from this study to the serology data from prior trials.

10. SPECIMEN MANAGEMENT

10.1 Laboratories

HPV16 and HPV18 serology will be analyzed in the HPV Immunology Laboratory of the National Cancer Institute led by [name].

10.2 Collection and Handling Procedures

Approximately 5 ml of blood will be drawn into a SST or tiger top Vacutainer tube at baseline and at months 6, 12, 18, 24, and 30 visits. The SST tube will be held at room temperature for 30 min and then centrifuged. One hundred (100) µl of serum will be aliquoted into each cryovial, filling as many cryovials as possible, and stored at -80°C. The cryovials will be labeled with study ID, subject ID, and visit date.

10.3 Shipping Instructions

All samples will be shipped in compliance with the International Air Transport Association (IATA) Dangerous Goods Regulations. Current shipper and institutional procedures must be followed. Biologic specimens (Category B, UN3373) will be in leak-proof primary and secondary receptacles with puncture

resistant packaging and absorbent material. Shipments are to be preceded with phone contact to the receiving lab to assure the shipment will be met and processed promptly.

Frozen serum cryovials will be shipped in batches overnight on dry ice to DCP Repository Contractor at the Frederick National Laboratory for Cancer Research (Leidos Biomedical Research, Inc.) for centralized storage and distribution for serological measurements.

10.4 Tissue Banking

Biologic specimens collected during the conduct of each clinical trial that are not used during the course of the study will be considered deliverables under the contract and thus the property of the NCI. At study completion, NCI reserves the option to either retain or relinquish ownership of the unused biologic specimens. If NCI retains ownership of specimens, the Contractor shall collect, verify and transfer the requested biologic specimens from the site to a NCI-specified repository or laboratory at NCI's expense.

11. REPORTING ADVERSE EVENTS

DEFINITION: AE means any untoward medical occurrence associated with the use of a drug in humans, whether or not considered drug related. An AE can therefore be any unfavorable and unintended sign), symptom, or disease temporally associated with participation in a study, whether or not related to that participation. This includes all deaths that occur while a participant is on a study.

Please note that all abnormal clinical laboratory values that are determined to be of clinical significance based on a physician's assessment are to be reported as AEs. Those labs determined to be of no clinical significance or of unknown clinical significance (per the physician's assessment) should not be reported as AEs. Any lab value of unknown clinical significance should continue to be investigated/followed-up further for a final determination, if possible.

A list of AEs that have occurred or might occur (Reported Adverse Events and Potential Risks) can be found in §6.2, Pharmaceutical Information, as well as the Investigator Brochure or package insert.

11.1 Adverse Events

11.1.1 Reportable AEs

All AEs that occur after the informed consent is signed and baseline assessments are completed (including run-in) must be recorded on the AE CRF (paper and/or electronic) including whether or not they are related to study agent.

11.1.2 AE Data Elements:

The following data elements are required for adverse event reporting.

- AE verbatim term
- System Organ Class (SOC)
- Common Terminology Criteria for Adverse Events v4.0 (CTCAE) AE term
- Event onset date and event ended date
- Severity grade
- Attribution to study agent (relatedness)
- Whether or not the event was reported as a serious adverse event (SAE)
- Whether or not the subject dropped due to the event
- Outcome of the event

11.1.3 Severity of AEs

11.1.3.1 Identify the AE using the CTCAE version 4.0. The CTCAE provides descriptive terminology (MedDRA lowest level term) and a grading scale for each adverse event listed. A copy of the CTCAE can be found at http://ctep.cancer.gov/protocolDevelopment/electronic_applications/ctc.htm

AEs will be assessed according to the CTCAE grade associated with the AE term. AEs that do not have a corresponding CTCAE term will be assessed according to the general guidelines for grading used in the CTCAE v4.0. as stated below.

CTCAE v4.0 general severity guidelines:

Grade	Severity	Description
1	Mild	Mild; asymptomatic or mild symptoms; clinical or diagnostic observations only; intervention not indicated.
2	Moderate	Moderate; minimal, local or noninvasive intervention indicated; limiting age-appropriate instrumental activities of daily living (ADL)*.
3	Severe	Severe or medically significant but not immediately life-threatening; hospitalization or prolongation of hospitalization indicated; disabling; limiting self-care ADL**.
4	Life-threatening	Life-threatening consequences; urgent intervention indicated.
5	Fatal	Death related to AE.

ADL

*Instrumental ADL refers to preparing meals, shopping for groceries or clothes, using the telephone, managing money, *etc.*

**Self-care ADL refers to bathing, dressing and undressing, feeding self, using the toilet, taking medications, and not bedridden.

11.1.4 Assessment of relationship of AE to treatment

The possibility that the adverse event is related to study agent will be classified as one of the following: not related, unlikely, possible, probable, definite.

11.1.5 Follow-up of AEs

All AEs, including lab abnormalities that in the opinion of the investigator are clinically significant, will be followed according to good medical practices and documented as such.

11.2 Serious Adverse Events

11.2.1 DEFINITION: Fed. Reg. 75, Sept. 29, 2010 defines SAEs as those events, occurring at any dose, which meet any of the following criteria:

- Death
- A life-threatening AE
- Inpatient hospitalization or prolongation of existing hospitalization
- A persistent or significant incapacity or substantial disruption of the ability to perform normal life functions

- A congenital abnormality or birth defect
- Important medical events that may not be immediately life-threatening or result in death or require hospitalization should also be considered serious when, based upon appropriate medical judgment, they may jeopardize the patient and may require intervention to prevent one of the other outcomes.

11.2.2 Reporting SAEs to DCP

11.2.2.1 The Lead Organization and all Participating Organizations will report SAEs on the DCP SAE form found at <http://prevention.cancer.gov/clinical-trials/clinical-trials-management/protocol-information-office/pio-instructions-and-tools/2012-consortia>.

11.2.2.2 Contact the DCP Medical Monitor by phone within 24 hours of knowledge of the event.

DCP Medical Monitor:

[name]

Chief, Lung & Upper Aerodigestive Cancer Research Group

Division of Cancer Prevention

National Cancer Institute

[name]

[name] (For FedEx, use [name])

[contact]

[contact]

Email: [contact]

Include the following information when calling the Medical Monitor:

- Date and time of the SAE
- Date and time of the SAE report
- Name of reporter
- Call back phone number
- Affiliation/Institution conducting the study
- DCP protocol number
- Title of protocol
- Description of the SAE, including attribution to drug

11.2.2.3 The Lead Organization and all Participating Organizations will email written SAE reports to DCP's Regulatory Contractor, CCS Associates, Inc. (CCSA [contact]) [contact] within 48 hours of learning of the event using the fillable PDF SAE Report Form.

11.2.2.4 The DCP Medical Monitor and regulatory staff will determine which SAEs require FDA submission.

11.2.2.5 The Lead Organization and all Participating Organizations will comply with applicable regulatory requirements related to reporting SAEs to the IRB/IEC.

11.2.3 Follow-up of SAE

Site staff should send follow-up reports as requested when additional information is available. Additional information should be entered on the DCP SAE form in the appropriate format. Follow-up information should be sent to DCP as soon as available. SAE related to the study agent will be followed until resolved, or deemed unlikely to further resolved by the Protocol Chair, or until the subject withdraws

consent for further follow-up. SAE unrelated or unlikely to be related to study agent will be followed for at least 30 days after the last dose of study agent.

12. STUDY MONITORING

12.1 Data Management

This study will report clinical data using the OnCore application from Forte Research Systems, Inc., as stated in the Master Data Management Plan. All users of the database will have appropriate education, training and experience to perform assigned tasks. The data collection and management will be done according to the Consortia 2012 DMP.

12.2 Case Report Forms

Participant data will be collected using protocol-specific case report forms (CRF) developed from the standard set of DCP Chemoprevention CRF Templates and utilizing NCI-approved Common Data Elements (CDE). The approved CRFs will be used to create the electronic CRF (e-CRF) screens in the OnCore application. Consortia site staff will enter data into the e-CRF for transmission to DCP according to pre-established DCP standards and procedures. Amended CRF will be submitted to the DCP Protocol Information Office for review and approval. Approved changes will be programmed into the OnCore database by the Consortium Data Management staff.

CRF Submission Information:

University of Arizona Early Phase Chemoprevention Consortium Office
Attn: [name]
[name]
[name]
[contact]
[contact]
Email: [contact]

12.3 Source Documents

Source documentation for this trial will consist of protocol-specific source documents as well as clinical and research laboratory reports. In the event of a Serious Adverse Event, medical records related to the event will be sought for source documentation of the event and its treatment, if any.

12.4 Data and Safety Monitoring Plan

The University of Arizona Cancer Center (UACC) Data and Safety Monitoring Board (DSMB) will provide oversight for subject safety for all UA Consortium clinical trials consistent with the National Institutes of Health Policy for Data and Safety Monitoring dated June 10, 1998; further guidance statement issued by the NIH on June 5, 2000, and the policy for Data and Safety Monitoring by Data and Safety Monitoring Boards. The UACC DSMB meets quarterly.

Regular monthly meetings of the UA Consortium, are used as a forum to review accrual rates, problematic issues relating to accrual and protocol implementation, adverse events occurrence, follow-up, and reporting; submission of all required study reports; and progress and outcomes of laboratory analyses.

12.5 Sponsor or FDA Monitoring

The NCI, DCP (or their designee), pharmaceutical collaborator (or their designee), or FDA may monitor/audit various aspects of the study. These monitors will be given access to facilities, databases, supplies and records to review and verify data pertinent to the study.

12.6 Record Retention

Clinical records for all participants, including CRFs, all source documentation (containing evidence to study eligibility, history and physical findings, laboratory data, results of consultations, *etc.*), as well as IRB records and other regulatory documentation will be retained by the Investigator in a secure storage facility in compliance with Health Insurance Portability and Accountability Act (HIPAA), Office of Human Research Protections (OHRP), Food and Drug Administration (FDA) regulations and guidances, and NCI/DCP requirements, unless the standard at the site is more stringent. The records for all studies performed under an IND will be maintained, at a minimum, for two years after the approval of a New Drug Application (NDA). For NCI/DCP, records will be retained for at least three years after the completion of the research. NCI will be notified prior to the planned destruction of any materials. The records should be accessible for inspection and copying by authorized persons of the Food and Drug Administration. If the study is done outside of the United States, applicable regulatory requirements for the specific country participating in the study also apply.

12.7 Cooperative Research and Development Agreement (CRADA)/Clinical Trials Agreement (CTA)

Not applicable.

13. STATISTICAL CONSIDERATIONS

13.1 Study Design/Description

This is a single-arm, open-label, non-randomized, phase IIA trial to determine the immunogenicity of a prime and deferred-booster dosing schedule of a nonavalent prophylactic HPV vaccine (GARDASIL 9) among 9-11 year-old girls and boys. The primary endpoint analysis will be evaluating persistence and stability of serologic geometric mean titers (GMT) of HPV16/18 between 6, 12, 18, and 24 months after the prime dose/prior to administration of the second dose. If the HPV 16/18 antibody level at 12/18/24 months is not inferior to the HPV 16/18/24 antibody level at 6/12/18 months at a non-inferiority margin of 0.35 standard deviation, then the serologic GMT is considered as persistent and stable.

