13.3 Accrual and Feasibility

We plan to accrue 143 eligible girls and 57 eligible boys to receive the deferred-booster schedule of the Gardasil 9. With an anticipated attrition rate of 30%, we expect to have at least 100 girls and 39 boys to complete the 30-month visit. We anticipate to enroll 6-8 participants/per month for each study site and estimate that it will take approximately 12-17 months to complete accrual.

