The protocol was originally designed to assess the serologic response in girls. Amendment 4 includes the addition of a cohort of boys. Due to limits in the study completion timeline and available study budget, a smaller number of boys than girls will be included in the study to generate pilot data on the serologic response in boys. Boys have been shown to mount a higher serologic response than girls. Therefore, we expect boys and girls to have different responses to the vaccine and will perform the primary analyses for girls and boys separately. For girls, with a sample size of 100 and an overall significance level of 5% (based on Bonferroni correction, i.e. a 1.67% significance level for each test), there will be at least 90% power to detect a non-inferiority margin no greater than 0.35 standard deviations [23]. For boys, with a sample size of 39 and an overall significance level of 5%, there will be at least 80% power to detect a non-inferiority margin no greater than 0.50 standard deviations. In addition, similar to the analysis performed by Safaeian et al. [13], we will also evaluate the stability by categorizing the changes in antibody level from 6 months to 12 months. Specifically, a participant's antibody level at 12 months either remains within two-fold of the level at 6 months (considered as stable) or decreases/increases more than two-fold of the level at 6 months (same for the changes from 12 months to 18 months and from 18 months to 24 months). Percentage of participants whose type-specific antibody levels decrease, increase, or remain stable between the 6 and 12 month study visits, between the 12 and 18 month study visits and between the 18 month and 24 month study visits will be reported along with the associated 95% confidence interval. For girls, a sample size of 100 will produce a two-sided 95% confidence interval with a width ≤ 0.203 based on the exact method approach. For boys, a sample size of 39 will produce a two-sided 95% confidence interval with a width ≤ 0.328 based on the exact method approach.

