13.5 Secondary Objectives, Endpoints, Analysis Plans

The secondary objectives include to determine the persistence and stability of serologic GMT of HPV types 6/11/31/33/45/52/58 between 6, 12, 18, and 24 months after prime dose and prior to the administration of the second dose and to assess safety and reactogenicity to each vaccine dose. The secondary endpoints are the antibody levels at 6, 12, 18, and 24 months for each HPV type. Similarly to the primary endpoint analysis, for evaluating persistence and stability of serologic GMT of each HPV type we propose to perform a one-sided paired t test to evaluate the difference in the mean of log-transformed antibody level between 6 and 12 months, between 12 and 18 months and between 18 and 24 months, respectively, to evaluate whether the GMT at 12/18/24 months is not inferior to the GMT at 6/12/18 months. In addition, percentage of participants whose type-specific antibody levels decrease, increase, or remain stable between the 6 and 12 month study visits, between the 12 and 18 month study visits and between the 18 and 24 month study visits will be reported along with the associated 95% confidence interval. A linear mixed effects model with BMI, time and the interaction between BMI and time as the covariates will be performed on antibody level data measured at 6, 12, 18, and 24 months to evaluate whether BMI affects the changes in each specific antibody level.

Similar to the primary analyses, we will perform all of the secondary and exploratory analyses separately for girls and boys. In addition, for all of the secondary and exploratory analyses, adjustment for multiple comparisons will not be performed. However, the number of comparisons will be reported and we will also cautiously interpret the findings. For both primary and secondary endpoints, if the normality assumption is violated, potential transformation will be sought or nonparametric methods such as signed rank test will be performed.

We will try to reduce the fraction of participants with missing outcomes as much as possible. The covariates (e.g. BMI, BSA, and sociodemographics) that are predictive of missing-ness for each outcome at each visit (i.e. 6, 12, 18 and 24 months) will be identified through use of logistic regression for each missing indicator and then incorporated into multiple imputation procedures to handle missing data while performing the statistical analysis for both primary and secondary endpoints.

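### The boys' non-inferiority margin is 0.35 SD in the Section 13.1 decision rule but 0.50 SD in the Section 13.4 power statement

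*Combined protocol and SAP*

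**What the plan says.** Section 13.1 describes the trial as one of a "nonavalent prophylactic HPV vaccine (GARDASIL 9) among 9-11 year-old girls and boys". It then gives the only decision rule in the documents: if the antibody level at 12, 18 or 24 months is not inferior to the level at the preceding visit "at a non-inferiority margin of 0.35 standard deviation, then the serologic GMT is considered as persistent and stable". It makes no exception by sex.

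Section 13.4 explains how boys came in. "The protocol was originally designed to assess the serologic response in girls"; Amendment 4 added a smaller cohort of boys to provide pilot data. Because boys are expected to respond more strongly, the investigators "will perform the primary analyses for girls and boys separately". The power statements are also split by sex. For girls, 100 participants give at least 90% power at 0.35 SD, which matches Section 13.1. For boys, with 39 participants and an overall 5% level, "there will be at least 80% power to detect a non-inferiority margin no greater than 0.50 standard deviations".

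The sample sizes come from Section 13.3: from 143 girls and 57 boys enrolled and 30% attrition, "we expect to have at least 100 girls and 39 boys to complete the 30-month visit".

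**The concern.** A reader who asks what result would make the boys' titers count as persistent and stable gets two answers. Section 13.1 says 0.35 SD. Section 13.4 points to 0.50 SD but never makes it a criterion. The likely cause is that Section 13.1 was left unchanged when boys were added, but the current text does not settle the matter.

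If Section 13.1 governs, the 80% power in Section 13.4 does not describe the test that will be run. If 0.50 SD governs, Section 13.1 is wrong for boys, and they are held to a looser standard than girls without the plan saying so. The trial is open-label and single-arm. If the choice is left until titers are known, a boys' result that lies between the two margins could be reported either way.

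**Working it through.** **Inputs from the documents**
- Test: one-sided paired t test on log antibody levels (13.4).
- Level: Bonferroni over three comparisons, 0.05/3 = 0.0167 each (13.4).
- Participants: 100 girls and 39 boys expected to complete; 57 boys enrolled (13.3, 13.4).
- Margins: 0.35 SD (13.1, and girls in 13.4); 0.50 SD (boys in 13.4).

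**Assumptions, not stated in the documents**
- The true change between visits is zero.
- SD means the SD of the paired log differences.

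**Formula.** For n pairs and margin m in SD units, power = P(T > t_crit), where T is noncentral t with n − 1 degrees of freedom and noncentrality m√n, and t_crit is the upper 1.67% point of the central t.

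**The plan's own figures**
- Girls, n = 100, m = 0.35: noncentrality 0.35 × 10 = 3.50, power 90.9% (stated: at least 90%).
- Boys, n = 39, m = 0.50: noncentrality 0.50 × 6.245 = 3.122, t_crit 2.208, power 81.6% (stated: at least 80%).

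Both are reproduced, so this is not a calculation error. The smallest margin that gives 80% power with 39 boys is 0.490 SD, which is close to the 0.50 SD in the plan.

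**Boys under the Section 13.1 margin of 0.35 SD**

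| Boys contributing | Noncentrality | Power per comparison |
|---|---|---|
| 39 | 2.186 | 49.7% |
| 57 (all enrolled) | 2.642 | 67.8% |
| 75 | 3.031 | 80.4% |

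Seventy-five is the smallest number that reaches 80%; 74 gives 79.8%. At 30% attrition, 75 evaluable boys means 75/0.70 = 107.1, so 108 enrolled, against 57 planned.

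**What passes.** An interval passes if the observed fall is less than m − t_crit/√n. With 39 boys, t_crit/√n = 2.208/6.245 = 0.354 SD.
- At 0.35 SD: 0.350 − 0.354 = −0.004. The observed GMT must rise slightly.
- At 0.50 SD: 0.500 − 0.354 = 0.146. An observed fall of up to 0.146 SD passes.

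Any observed fall from 0 to 0.146 SD therefore passes under one section and fails under the other. With 57 boys, t_crit is 2.182 and the 0.35 SD rule allows a fall of up to 0.35 − 2.182/7.550 = 0.061 SD.

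**How much looser 0.50 SD is.** If the true decline is 0.35 SD, the 0.35 SD rule passes 1.67% of the time by construction. The 0.50 SD rule with 39 boys has noncentrality (0.50 − 0.35) × 6.245 = 0.937 and passes 11.1% of the time.

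**If SD means a per-visit SD.** The margin is then divided by √(2(1 − ρ)), where ρ is the within-person correlation. At ρ = 0.5 the divisor is 1 and every figure above is unchanged. For assumed ρ of 0.3 to 0.7, boys' power at 0.35 SD runs from 36.9% to 72.9% with 39 boys and from 52.4% to 88.8% with 57.

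**The case against.** The strongest reply is that there is no rival criterion. Section 13.1 holds the only decision rule and names boys, so 0.35 SD governs. Section 13.4 merely reports the margin that 39 boys can support, which the 0.490 SD figure bears out. This is a fair reading, but it does not rescue the text. The only power quoted for boys would then not be the power of their test, and the phrase "at least 80% power to detect a non-inferiority margin no greater than 0.50 standard deviations" does not help: read literally it takes in 0.35 SD, where 80% is untrue. The opposite reading, that the later and sex-specific passage governs boys, is just as natural.

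Second, the boys are declared a pilot cohort, the girls' analysis is untouched, and boys also have the two-fold change analysis, which uses no margin. All of this stands and limits the consequence. But Section 13.4 still gives boys the primary test, a 5% overall level and a power claim, and the pilot label does not name the margin.

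Third, 39 is the number expected at month 30, whereas the primary comparisons end at month 24, and Section 13.5 plans "multiple imputation procedures to handle missing data while performing the statistical analysis for both primary and secondary endpoints". The number of pairs could therefore exceed 39; power at 0.35 SD would be about 56% with 45 boys and 61% with 50. The figure for 57 is an upper bound, because imputation does not replace lost information fully. None of these reaches 80%.

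Finally, the 11.1% is not an inflated error rate. If 0.50 SD is the intended margin, a decline of 0.35 SD is acceptable by definition. The figure shows only how far apart the two rules are.

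**Conclusion.** The concern holds. Two sections of the current text give different margins for boys and nothing reconciles them. Either the stated 80% is not the power of the Section 13.1 rule, which is about 50% per comparison with 39 boys and at most about 68% with all 57, or the Section 13.1 margin is wrong for boys.

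These figures assume no true decline and the SD of paired log differences, the reading that fits a paired t test and reproduces both stated powers. Under a per-visit SD the size of the power gap depends on the correlation, and with high correlation and nearly complete data power at 0.35 SD could exceed 80%. The textual conflict does not depend on any of these assumptions. The point should be fixed; it affects boys only and leaves the girls' conclusion intact.

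**What to change.** Before analysis, state in Section 13.1 the margin that applies to each sex, and make Section 13.4 agree.
- If 0.35 SD applies to boys, restate their power as about 50% per comparison with 39 boys (about 68% if all 57 contribute). Given the pilot purpose, the sponsor may then prefer to lead the boys' results with GMT ratios and 95% confidence intervals.
- If 0.50 SD applies to boys, write it into the Section 13.1 rule, justify it, and report that their criterion is looser than the girls'.

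It would also help to say in the same sentence which SD the margin refers to, although the conflict can be resolved without it.

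The cost is wording in two sections, with no change to visits, samples or enrolment. The price is either a lower stated power for boys or an openly looser criterion for them.

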13.4 Primary Objective, Endpoint(s), Analysis Plan

The primary objective of this study is to determine the persistence and stability of serologic geometric mean titer (GMT) of HPV 16/18 between 6, 12, 18, and 24 months after the prime dose and prior to the

administration of the second dose. The primary endpoints are the HPV 16/18 antibody levels at 6, 12, 18, and 24 months. To address the primary objective, the primary endpoint analysis will be evaluating persistence and stability of serologic geometric mean titers (GMT) of HPV16/18 between 6, 12, 18, and 24 months after the prime dose/prior to administration of the second dose. We first propose to perform a one-sided paired t test to compare the difference in the mean of the log-transformed antibody levels between 6 and 12 months, between 12 and 18 months, and between 18 and 24 months respectively, to evaluate whether the GMT at 12/18/24 months, respectively, is not inferior to the GMT at 6/12/18 months. Comparing the difference in the mean of the log-transformed antibody levels is equivalent to comparing the logarithm of the ratio of GMTs since GMT is equal to the exponentiation of log-transformed mean. Bonferroni correction will be used to correct for multiple comparisons (6 vs. 12, 12 vs. 18 and 18 vs. 24).

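### The margin that decides whether titres persist is 0.35 of an undefined SD with no GMT ratio attached, and boys are given two different margins

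*Combined protocol and SAP*

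**What the plan says.** Section 13.1 describes a trial in girls and boys and gives one decision rule. Titres count as persistent and stable if the antibody level at 12, 18 and 24 months is non-inferior to the level six months before, "at a non-inferiority margin of 0.35 standard deviation".

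Section 13.4 gives the test: a one-sided paired t test on log-transformed levels for each of three steps (6 to 12, 12 to 18 and 18 to 24 months), Bonferroni-corrected to 1.67% each. It notes that "Comparing the difference in the mean of the log-transformed antibody levels is equivalent to comparing the logarithm of the ratio of GMTs", but gives no ratio as the margin.

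The same section states the power by sex:
- 100 girls: "there will be at least 90% power to detect a non-inferiority margin no greater than 0.35 standard deviations".
- 39 boys: "there will be at least 80% power to detect a non-inferiority margin no greater than 0.50 standard deviations".

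It explains that boys were added by amendment to provide pilot data, and that "we expect boys and girls to have different responses to the vaccine and will perform the primary analyses for girls and boys separately". It also reports the percentage of participants whose level stays within two-fold or moves beyond it, with confidence intervals but no pass threshold.

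Section 13.5 adds that if normality fails, a transformation will be sought or "nonparametric methods such as signed rank test will be performed".

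**The concern.** The primary objective is persistence of the GMT, so a pass should let a reader say how much GMT loss has been ruled out. A margin in SD units does that only if the SD is named and has a value. Four things are left open: which SD it is, its size, whether it is set in advance or taken from the trial data, and the GMT ratio that results. Until they are settled, the main conclusion has no defined magnitude.

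Under one reading the consequence is worse. If the SD is that of the paired log change and is estimated from the same data, it cancels out of the test. Only a standardised fall is then tested, and when titres have really fallen, noisier data pass more easily.

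Boys raise a separate question. The rule in 13.1 names no sex and uses 0.35 SD, while 13.4 calls 0.50 SD a non-inferiority margin for boys. The same boys' data can pass under one and fail under the other.

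**Working it through.** **Inputs from the plan.** 100 girls and 39 boys evaluable; one-sided alpha 0.05/3 = 0.0167 per test; margins 0.35 SD (13.1, and girls in 13.4) and 0.50 SD (boys in 13.4). A true change of zero is assumed for power. The documents give no SD, so every ln SD below is an assumption.

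**Step 1: reproduce the stated power.** Noncentral t with n − 1 degrees of freedom and noncentrality k√n, where k is the margin in SDs of paired change.

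| Group | k√n | critical t | power | paired t needed to pass if the SD is estimated (critical t − k√n) |
|---|---|---|---|---|
| Girls, n = 100, k = 0.35 | 3.500 | 2.158 | 0.909 | −1.34 |
| Boys, n = 39, k = 0.50 | 3.122 | 2.208 | 0.816 | −0.91 |
| Boys, n = 39, k = 0.35 | 2.186 | 2.208 | 0.497 | +0.02 |

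The first two rows match the stated 90% and 80%, so the power arithmetic is sound.

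**Step 2: does that identify the SD?** No. If the SD is that of the log level, with correlation rho between visits, 0.35 level-SDs equal 0.35/√(2(1 − rho)) SDs of paired change. Girls' power is then 0.787, 0.909 and 0.990 at rho 0.3, 0.5 and 0.7. A claim of at least 90% fits the level reading at rho 0.5 and above.

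**Step 3: what the margin means as a GMT ratio.** Taking s as the SD of paired natural-log change, the ratio is exp(−k × s).

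| Assumed s | 0.35 SD | 0.50 SD |
|---|---|---|
| 0.3 | 0.90 | 0.86 |
| 0.5 | 0.84 | 0.78 |
| 1.0 | 0.70 | 0.61 |
| 1.5 | 0.59 | 0.47 |

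**Step 4: the reversal, if s is the paired-change SD estimated from the trial.** Girls pass when paired t is at least −1.34, whatever s is.
- *Observed ratio 0.90.* The lower one-sided 98.33% limit is exp(ln 0.90 − 2.158 × s/10). At s = 0.5 it is 0.808 against a margin of 0.839 (t = −2.11), which fails. At s = 1.0 it is 0.725 against 0.705 (t = −1.05), which passes. The data that exclude more waning are the ones that fail.
- *True ratio 0.80, one step.* The pass probability is P(noncentral t, 99 df, noncentrality 10 × ln 0.80/s, ≥ −1.342) = 0.001, 0.187 and 0.441 at s = 0.5, 1.0 and 1.5.
- *Contrast with a fixed ratio limit of 0.67 (illustration only).* P(noncentral t, noncentrality 10 × ln(0.80/0.67)/s, ≥ 2.158) = 0.916, 0.354 and 0.169. More noise now makes passing harder. The two margins coincide at s = −ln(0.67)/0.35 = 1.14; below that, 0.35 SD is the stricter.

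**Step 5: all three steps.** If every step must pass and the steps were independent, the probabilities at s = 1.0 and 1.5 are 0.187³ = 0.007 and 0.441³ = 0.086. If visit noise is independent, adjacent changes are negatively correlated and the figures drop to about 0 and 0.02.

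**Step 6: boys.** From step 1, a paired t between −0.91 and +0.02 passes at 0.50 SD and fails at 0.35 SD. At 0.35 SD any observed fall fails. For 80% power at 0.35 SD, 75 evaluable boys would be needed, or 75/0.70, rounded up to 108 accrued, against the planned 57.

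**The case against.** **The rule does not necessarily reward noise.** A reader might infer from step 4 that, as written, noisier titres always make a loss easier to pass. The documents do not support that. It needs both the paired-change SD and estimation from the trial, and neither is stated. If the SD is fixed in advance, more noise makes passing harder, as usual. If it is the SD of the log level, the reversal need not occur. In a simulation with 100 girls, a true ratio of 0.80, the SD estimated from the earlier visit and an assumed between-child ln SD of 1.0, the pass probability fell with noise: 0.76, 0.46 and 0.40 at paired ln SD 0.5, 1.0 and 1.5. With between-child SD 0.7 it rose only mildly (0.14, 0.19, 0.25). This objection stands, so the reversal is conditional.

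**The matching powers do not settle the reading.** A reader might take them as proof of the paired-change SD; step 2 shows they are not. A reference is cited beside the girls' figure, but its entry is not in the available text and nothing is inferred from it.

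**Single-step rates are not the risk of a wrong overall verdict.** 13.1 can be read as requiring all three steps, which makes a wrong pass much rarer (step 5).

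**The largest figures need wide SDs.** At paired ln SD 1.5 with no mean change, only 36% of children would stay within the plan's two-fold band, against 51% at 1.0 and 83% at 0.5. At 0.5 the rule is strict. This limits the likely size of the problem but does not supply the missing value.

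**The two-fold percentages would show large waning.** They would help, but they classify individuals and decide nothing.

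**Boys.** Section 13.1 may be girls-only text left unchanged when boys were added, and 0.50 SD appears in a power statement. That is plausible, so a firm claim that the plan sets two decision rules for boys goes too far. Still, 13.1 as it reads covers both sexes.

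**Conclusion.** The concern holds in a limited form. The pass/fail margin is defined by an SD that the plan does not identify, quantify or convert to a GMT ratio, so the conclusion of persistence excludes no stated loss. Over assumed paired ln SDs of 0.3 to 1.5, the tolerated ratio per six-month step runs from 0.90 to 0.59. This does not depend on how the reversal question is settled.

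The reversal is a conditional risk. It follows from the most natural reading of a paired t test, but the documents do not confirm that reading.

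For boys, the unresolved choice between 0.35 and 0.50 SD moves power from 0.497 to 0.816 and can change the verdict. It is a smaller matter, settled by one sentence.

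The signed-rank fallback needs a numeric log-scale shift to serve as a non-inferiority test. Its absence follows from the same omission and is not a further defect. The design and the stated power calculations are not in error. This should be fixed, but it does not invalidate the trial.

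**What to change.** Before later-visit titres are analysed:

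1. State in 13.1 and 13.4 a pre-specified lower limit for the later/earlier GMT ratio, chosen and justified by the sponsor. Declare non-inferiority when the lower one-sided 98.33% confidence limit exceeds it. Use the log of the same limit as the shift in any signed-rank fallback in 13.5.
2. At minimum, if the SD form is kept, name the SD, fix its numeric value in advance and print the GMT ratio it equals. Section 9.2 points to a possible source: "The VLP ELISA assays have been used previously to measure HPV16/18 serology in prior HPV vaccine trials".
3. State one margin for boys so that 13.1 and 13.4 agree.
4. Show power by sex over a range of SDs. For illustration, with a limit of 0.67 and no true change, girls and boys have power of 0.966 and 0.617 at ln SD 1.0, and 0.695 and 0.305 at ln SD 1.5.

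The cost is wording in 13.1 and 13.4, a line in 13.5 and a short table, with no new visits, samples or participants. The downside is that once the limit is fixed, power depends on the true SD. At 1.25 and 1.5 times the assumed SD, girls' power (0.35 SD) falls from 0.909 to 0.739 and 0.571, and boys' (0.50 SD) from 0.816 to 0.616 and 0.457.
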